### 5.3.3 Growth data

Table 5-5 summarizes the time windows for growth data, where windows are centered at every 6 months after start of deferasirox. If there is more than one assessment within the time window, the last available assessment in that time window will be used. Although height and weight could be collected more frequently than every 6 months, this choice of time window length was made to reflect the degree of accuracy in the reference values (every 6 months) that will be used in the calculation of summary variables of growth (Section 2.7.7).

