**Table 5-5 Time windows for growth data**

Assessment	Time window
Baseline	Treatment Days up to 1
Month 6	Treatment Days 85 – 252
Month 12	Treatment Days 253 – 420
Month 18	Treatment Days 421 – 588
Month 24	Treatment Days 589 – 756
Month 30	Treatment Days 757 – 924
Month 36	Treatment Days 924 – 1092
Month 42	Treatment Days 1093 – 1260
Month 48	Treatment Days 1261 – 1428
Month 54	Treatment Days 1429 – 1596
Month 60	Treatment Days 1597 – 1764
etc.	
Treatment Day 1 = date of first intake of deferasirox	

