## 5.4 Month/year derivation

For all derivations, a year will be defined as 365.25 days and a month will be calculated as  $(365.25 / 12) = 30.4375$  days. If duration is to be reported in months, duration in days will be divided by 30.4375.

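### Growth windows in the final SAP are built on 28-day months, against the SAP's own six-month centring and 30.4375-day month, so labels from Month 36 on miss their anniversary and day 924 is counted twice

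*SAP*

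**What the plan says.** Three parts of the final SAP bear on this.

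- Section 5.3.3 states that "windows are centered at every 6 months after start of deferasirox". It says the window length was chosen to suit reference values given every 6 months, and it selects the last available assessment in each window.
- Table 5-5 gives the bounds. Month 6 is "Treatment Days 85 – 252", Month 36 is "Treatment Days 924 – 1092" and Month 60 is "Treatment Days 1597 – 1764". The table continues beyond Month 60 and counts from "Treatment Day 1 = date of first intake of deferasirox".
- Section 5.4 states "For all derivations, a year will be defined as 365.25 days", takes one twelfth of that as a month, and says that for durations in months "duration in days will be divided by 30.4375".

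Section 2.7.7.1 uses the windows. It summarises height and BMI at 6-month intervals over the core and extension phases, with descriptive statistics by time window, box plots, and counts of patients below the 5th or above the 95th percentile. Neither Section 5.3.3 nor Table 5-5 says that a growth month is 28 days.

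**The concern.** A window described as centred on a six-month mark should have that mark in its middle. Table 5-5 does not achieve this, and the gap grows with follow-up. A reader of the growth tables will take Month 36 to mean three years of treatment and Month 60 to mean five. In the later rows the label runs ahead of the data, and an assessment made on the true anniversary is reported under the next label.

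These late rows matter because the extension exists to collect long-term safety data. It may run to Week 305, and the rationale for protocol Amendment 6 reports 67 patients still in the extension on 24 June 2021. All patients had completed the core phase by 18 December 2018. With 336 days of core treatment plus the 919 days between those two dates, those patients were at least about 1,255 days, or 41 months, from first dose.

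The shared day is a separate slip. If a visit on day 924 were the only one in the Month 36 window, the same measurement would serve both Month 30 and Month 36, and the interval for velocity would be zero days. The planned 4-weekly visit is day 925 (28 × 33 + 1), so a visit one day early is enough to land on day 924.

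**Working it through.** **Inputs.** Window bounds and Day 1 from Table 5-5; 1 month = 365.25/12 = 30.4375 days from Section 5.4; the centring statement from Section 5.3.3.

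**Step 1: reproduce the table.** With a 28-day month, the window for label m is 28m − 83 to 28m + 84.
- m = 6: 168 − 83 = 85 and 168 + 84 = 252, as printed.
- m = 60: 1680 − 83 = 1597 and 1680 + 84 = 1764, as printed.
- m = 36: 1008 − 83 = 925 and 1008 + 84 = 1092. The table prints 924 as the lower bound.

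This rule gives all ten rows. The only difference is 924 in place of 925.

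**Step 2: place the true anniversaries.** With first intake as Day 1, m months is day 30.4375m + 1. The centre in months is (midpoint − 1)/30.4375.

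| Label | Printed window | Centre (months) | True m-month day | Falls in |
|---|---|---|---|---|
| 6 | 85–252 | 5.5 | 183.625 | Month 6 |
| 12 | 253–420 | 11.0 | 366.25 | Month 12 |
| 18 | 421–588 | 16.5 | 548.875 | Month 18 |
| 24 | 589–756 | 22.1 | 731.5 | Month 24 |
| 30 | 757–924 | 27.6 | 914.125 | Month 30 |
| 36 | 924–1092 | 33.1 | 1096.75 | Month 42 |
| 42 | 1093–1260 | 38.6 | 1279.375 | Month 48 |
| 48 | 1261–1428 | 44.1 | 1462 | Month 54 |
| 54 | 1429–1596 | 49.7 | 1644.625 | Month 60 |
| 60 | 1597–1764 | 55.2 | 1827.25 | Month 66 (implied, 1765–1932) |

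**Step 3: find where it breaks.** The drift is 30.4375 − 28 = 2.4375 days per labelled month. The anniversary passes the upper bound when 2.4375m + 1 > 84, that is m > 34.1; without the added day, m > 84/2.4375 = 34.5. Either way Month 36 is the first label affected. A shift of two windows would need m > 252/2.4375 = 103, beyond the 305-week maximum.

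**Step 4: find which value is used.** On planned 4-weekly visits (days 28k + 1), the last visit in each window is:
- Month 6: day 225, 224/30.4375 = 7.4 months
- Month 36: day 1065, 1064/30.4375 = 35.0 months
- Month 60: day 1737, 1736/30.4375 = 57.0 months

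**Step 5: check the annual examinations.** Week 205 is day 204 × 7 + 1 = 1429, or 46.9 months, and falls in the Month 54 window. Week 257 is day 1793, or 58.9 months, and falls in the implied Month 66 window.

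**The case against.** The best defence is that the 28-day month is a convention of this study. Protocol Table 7-2 calls the 4-weekly extension measurements of height and weight monthly, and the drug-exposure periods in Section 5.3.1 of the final SAP define Month 1 as days 1 to 28. Table 5-5 may well be deliberate. That stands as an explanation and supports keeping the grid under other labels. It does not remove the conflict: the exposure convention is not extended to growth, Section 5.4 makes no exception, and the height-velocity formula in Section 5.6 itself takes half of 365.25 days as six months.

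The last-available rule also offsets much of the later drift. On planned visits the Month 60 value is taken at 57.0 months rather than at the 55.2-month centre. That stands too, although the same rule pushes Month 6 out to 7.4 months. The rule is explicit and is a choice, not an error. The laboratory and ocular windows take the assessment closest to the planned visit, but nothing requires growth to match them.

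A reader might infer more than the documents support:
- **Velocity compared with the wrong reference.** It may seem that a 6-month velocity reference is applied to 24-week increments. Section 5.6 computes velocity from the actual assessment dates with a half-year factor, evidently so as to express it per six months whatever the gap. The way that formula is bracketed in print is a separate question.
- **Individual scores wrong.** Height and BMI scores are looked up from the patient's exact age, and velocity scores from age at the assessment date, not from the window label.
- **Month 60 data lost.** The table continues past Month 60, so an assessment at true month 60 goes to the following window.

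**Conclusion.** The inconsistency is real and minor. Table 5-5 does not carry out the centring that Section 5.3.3 describes under the month that Section 5.4 defines. By window centre, the labels overstate time on treatment by 0.5 month at Month 6, rising to 4.8 months at Month 60 (60 − 55.2). On planned visits with the stated selection rule, the value used is 1.4 months late at Month 6, 1.0 month early at Month 36 and 3.0 months early at Month 60. Day 924 is assigned twice, which is an error under either month length.

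The consequence is limited to time-point labels and to which assessments are selected and summarised together. The outputs are descriptive, and the same windows apply to both treatment columns. No hypothesis test depends on them.

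The figures assume that Section 5.4 governs growth months, since no exception is stated. The figures for selected values also assume visits on their planned 4-weekly days.

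**What to change.** Choose one of two corrections to the final SAP.

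1. **Keep the month labels and replace the bounds.** Centre window m on day 30.4375m + 1, running from the first whole day on or after 30.4375(m − 3) + 1 to the last whole day before 30.4375(m + 3) + 1. This gives Month 6 = 93–274, Month 12 = 275–457, Month 18 = 458–640, Month 24 = 641–822, Month 30 = 823–1005, Month 36 = 1006–1188, Month 42 = 1189–1370, Month 48 = 1371–1553, Month 54 = 1554–1735 and Month 60 = 1736–1918. The windows are contiguous and share no day.
2. **Keep the 4-weekly grid.** Relabel the rows by weeks of treatment (Week 24, Week 48 and so on), amend the six-month centring text in Section 5.3.3 to match, and change the Month 36 lower bound from 924 to 925.

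Taking the assessment nearest the target day, as the laboratory and ocular windows do, would suit centred windows better but is optional.

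The cost is one table, a sentence of text under option 2, and a rerun of the growth summaries if they have already been programmed. No new data are needed.

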**Table 5-5 Time windows for growth data**

Assessment	Time window
Baseline	Treatment Days up to 1
Month 6	Treatment Days 85 – 252
Month 12	Treatment Days 253 – 420
Month 18	Treatment Days 421 – 588
Month 24	Treatment Days 589 – 756
Month 30	Treatment Days 757 – 924
Month 36	Treatment Days 924 – 1092
Month 42	Treatment Days 1093 – 1260
Month 48	Treatment Days 1261 – 1428
Month 54	Treatment Days 1429 – 1596
Month 60	Treatment Days 1597 – 1764
etc.	
Treatment Day 1 = date of first intake of deferasirox	

### 5.3.4 Ocular data

Ocular data will be collected at screening visit, at patient visit 11 and at end of treatment visit during the core phase and annually during the extension phase. If two or more assessments are performed within a time window then the assessment closest to the planned visit is used in analyses by time window. When two values are equidistant from the planned assessment, the later one is used in analyses.

For worst post-baseline assessment, all on-treatment values are considered regardless of time windows.

[Table 5-6](#) and [Table 5-7](#) show the defined time windows.

**Table 5-6 Time windows for ocular data in core phase**

Time Window	Planned Visit Timing	Time Window Definition
On treatment		
Baseline	On or before Study Day 1*	≤ Study Day 1
Week 25	Study Day 169	Study Days 140 – 197
EOT_Core	NA	

- EOT-core visit are included if obtained within the next 14^ days of last non-0 dose intake (^NA if patients continuing in extension phase).

- Week 49 visit for patients continuing into extension

- For the post-baseline assessments, if no data were collected at the EOT visit the last available post-baseline data on or before the last non-zero dose will be used for EOT - Core.

\*Study Day 1 = first day of study treatment

**Table 5-7 Time windows for ocular data in extension phase**

Time Window	Planned Visit Timing	Time Window Definition
On treatment		
Baseline	On or before Study Day 1*	≤ Study Day 1

Time Window	Planned Visit Timing	Time Window Definition
On treatment		
Week# y=5+4*k with (k = 24, 37,...to 89 with increments of 13)	Study Day (5+4*k-1)*7+1	Study Days (5+4*k-1)*7+1-59 to (5+4*k-1)*7+1+58
EOT_Ext	NA	
 
- EOT-ext visit are included if obtained within the next 14 days of last non-0 dose intake
 
- For the post-baseline assessments, if no data were collected at the EOT visit the last available post-baseline data on or before the last non-zero dose will be used for EOT - Ext.
 

\*Study Day 1 = first day of study treatment

# Every 52 weeks starting from Week 101

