## **7 Visit schedule and assessments**

### **7.1 Study flow and visit schedule**

[Table 7-1](#) lists all of the assessments for the core phase and [Table 7-2](#) lists all of the assessments for the optional extension phase and both indicate with an "X", the visits when they are performed. Patients in the core phase who complete Visit 16 and decide to proceed to the optional extension phase will begin following all the assessments included in the visit 777 in [Table 7-1](#) and then follow the optional extension assessment visit 17 listed in [Table 7-2](#) on the

same day so as to avoid a gap in treatment. Patients who were on the DT arm during core phase of study who have switched to granules at Visit 17 as part of the optional extension phase will need to return weekly (Visits 18, 19 and 20) for the first month after beginning the optional extension phase (granules) for serum creatinine and creatinine clearance. Thereafter they will follow the same schedule as patients who were on granules arm during the core phase. Visit 778 should not be completed by patients who continue into the optional extension phase. Should a patient discontinue the core phase at or prior to Visit 16, they should perform Visits 777 and 778 including safety follow up as per [Table 7-1](#).

Patients in the optional extension phase will complete Visit 779 and 780 at the end of the study or in case of earlier discontinuation.

Patients should be seen for all visits to perform the scheduled assessments on the designated day, or as close to is as possible, i.e., for the core phase not exceeding  $\pm$  2 days for assessments scheduled in Visits 1 to 6 and  $\pm$  7 days for all other visits until End of Treatment Visit 777. For the optional extension phase, not exceeding  $\pm$  7 days for all visits until End of Treatment Visit 779. In this clinical trial, a week is 7 calendar days. For yearly assessments in extension phase, i.e. audiology, ocular and growth and development examinations,  $\pm$  30day window is allowed.

All visits should be scheduled respective to the randomization date (Visit 3) for the core phase, rather than in relation to the previous visits. For the optional extension phase, all visits should be scheduled respective to Visit 17.

All data obtained from these assessments must be supported in the patient's source documentation. No eCRF pages will be used as a source document.

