### **2.1.2 Study drug and study treatment**

The terms study drug and study treatment are equivalent and will refer to deferasirox granule.

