### **2.1.4 Study day**

The study day **for safety** (e.g. adverse event onset, laboratory abnormality occurrence, vital sign measurement, Electrocardiogram (ECG), etc.) will be calculated using the start date of study treatment as the reference. For assessments occurring

- **on or after the start date of study treatment**, the study day will be calculated as (date of safety assessment) – (start date of study treatment) + 1. Study day 1 will therefore be the first day of study treatment.
- **before the start date of study treatment**, the study day will be calculated as (date of safety assessment) – (start date of study treatment).

For example, if an adverse event starts 3 days before the start of study treatment the study day displayed on the listing will be negative, i.e. -3.

The study day will be displayed in the data listings.

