### **2.1.5 Baseline**

Baseline is considered as the result of an investigation describing the ‘true’ uninfluenced state of the patient.

For **safety evaluations** (e.g. laboratory, vital signs, etc.) the last available (i.e. non-missing) assessment before or on the date of start of study treatment is taken as ‘baseline’ value or ‘baseline’ assessment.

If patients have no value as defined above, the baseline result will be missing. Unscheduled assessments will be considered in the determination of baseline.

For safety assessments, if an assessment is planned to be performed prior to the first dose of study drug in the protocol and the assessment is performed on the same day as the first administration of study drug, it will be assumed that it was performed prior to study drug administration, if assessment time point is not collected or is missing.

Patients who start treatment and discontinue from the study on the same day may have 2 different sets of data collected on study Day 1, one being reported to the week 1 visit, the other reported to the End Of Treatment (EOT) visit. Data reported at the EOT visit are not eligible for baseline selection.

For analyses of the entire granule period requiring comparison to baseline value (e.g. lab shift tables, pubertal staging etc.) the baseline is defined as follows. For patients randomized to DT formulation who switched to granule formulation in the extension phase, the date of the last assessment prior or equal to the start date of granules in the extension phase will be defined as pre-granule value which will be reference value for changes in the extension time. For patients randomized to granules continuing in extension phase the initial baseline value at study start will be taken.

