### **2.1.6 On-treatment period**

The overall observation period will be divided into three mutually exclusive segments taking into account stop rules as per [Table 2-1](#):

- Pre-treatment period: from day of patient's first informed consent to the day before first dose of study drug;
- On-treatment period: from day of first dose of study drug to 30 days after last dose of study drug.
- Post-treatment period: starting at day 30+1 after last dose of study treatment.

For the entire granule period, the following conventions will be taken into account while deriving the three observation periods above:

- For patients enrolled in DT formulation in the core phase, the pre-treatment period will not be derived, and their entire granule period starts from Extension phase start date mentioned in [Table 2-1](#)
- For patients enrolled in Granule formulation in the core phase, the first dose of study drug will be the day of first dose in the core phase.

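### Final SAP Table 5-7: counted from the first granule dose, cross-over patients' first annual extension eye examination (day 365) fits no weekly window, because the windows start at day 642

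*SAP*

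**What the plan says.** Final SAP, section 5.3.4, Table 5-7 has a Baseline row, a series of weekly windows and an end-of-extension row (EOT_Ext). The weekly windows are "Every 52 weeks starting from Week 101", with limits "Study Days (5+4*k-1)*7+1-59 to (5+4*k-1)*7+1+58" for k = 24, 37 and so on to 89. The footnote gives the origin: "Study Day 1 = first day of study treatment".

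Three other sections of the final SAP fix what that origin means:
- 2.1.2: "The terms study drug and study treatment are equivalent and will refer to deferasirox granule".
- 2.1.4: the study day for safety data "will be calculated using the start date of study treatment as the reference".
- 2.1.6: for patients on DT in the core phase, "their entire granule period starts from Extension phase start date mentioned in" Table 2-1.

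For baseline, 2.1.5 says that the last assessment up to the start of granules in DT switchers "will be defined as pre-granule value which will be reference value for changes in the extension time".

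In the protocol, section 7.1 says "For the optional extension phase, all visits should be scheduled respective to Visit 17" and allows 30 days either way for yearly extension assessments. Section 7.1.2 places Visit 17 on the same day as the Week 49 core visit. Table 7-3 puts the first extension eye photographs at Visit 33, Week 101, and then yearly.

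**The concern.** The label Week 101 is the protocol's name for Visit 33, counted from randomization. The windows reproduce that count, but the final SAP's definitions start a cross-over patient's count about 48 weeks later. If the text is programmed as written, that group's first on-granule annual examination has no weekly window.

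The outputs at stake are those presented by visit or timepoint in section 2.7.6:
- assessment-completion counts;
- logMAR shifts;
- slit lamp counts and by-visit shifts;
- intraocular pressure summaries and shifts;
- fundus oculi counts;
- colour fundus photography findings and image quality;
- lens image quality.

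The two groups are shown side by side. The Week 101 column would therefore set the granule arm's first extension examination against the cross-over group's second, and completion counts would understate the examinations done. Protocol Amendment 6 was written to answer a health authority request for ophthalmic data up to 2 years, and Visit 33 is the scheduled examination nearest that point after randomization.

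**Working it through.** **Inputs.** Window index and limits: Table 5-7. Origin: final SAP 2.1.2, 2.1.4 and 2.1.6. Extension entry at Week 49: protocol 7.1.2. Annual examinations from Week 101: protocol Table 7-3. Tolerance of 30 days: protocol 7.1. I assume that the first granule dose is taken on the day of Visit 17.

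**The plan's own label.** Week = 5 + 4k, and k = 24 gives 5 + 96 = 101, as stated.

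**Windows.** Planned day = (week − 1) × 7 + 1; limits are planned day − 59 to planned day + 58.
- Week 101: 100 × 7 + 1 = 701, window 642 to 759.
- Week 153: 152 × 7 + 1 = 1065, window 1006 to 1123.
- Week 205: 204 × 7 + 1 = 1429, window 1370 to 1487.
- Week 257: 256 × 7 + 1 = 1793, window 1734 to 1851.

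**Two clocks.** Week 49 is core day 48 × 7 + 1 = 337. Granule day of a cross-over visit = core day − 337 + 1.

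| Scheduled examination | Core day | Window on core clock | Granule day (± 30) | Window on granule clock |
|---|---|---|---|---|
| Week 101 (Visit 33) | 701 | Week 101 | 365 (335–395) | none |
| Week 153 | 1065 | Week 153 | 729 (699–759) | Week 101 |
| Week 205 | 1429 | Week 205 | 1093 (1063–1123) | Week 153 |
| Week 257 | 1793 | Week 257 | 1457 (1427–1487) | Week 205 |

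The miss is not marginal: even at the late end of the tolerance, day 395 is 642 − 395 = 247 days short of the first window. A granule start later than Visit 17 would lower the granule day further. For patients randomized to granules the two clocks coincide, so Visit 33 is day 701 and is labelled as intended.

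**Where the mismatch comes from.** Table 4-5 of the End of Core SAP has the same window formula. There, section 2.6 defines study treatment as either DT or granules, so day 1 is the first core dose and Week 101 fits. The final SAP narrowed the definition and kept the windows.

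**The companion table.** Table 5-6 carries the same footnote, but its Week 25 window (days 140 to 197) and Week 49 entry are core visits. The final SAP analyses lens and colour fundus photographs on Safety Sets 1 to 3, which include DT patients' core data. For them, Table 5-6 works only if day 1 is the first DT dose.

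**The case against.** The strongest reply is that Table 5-6 shows that the granule-only definition cannot have been meant for the ocular windows. On the core clock, every annual examination falls in its own window and nothing is lost. That is right as far as it goes. A reader might infer that the core clock cannot rescue Table 5-7 because its Baseline row would become the pre-DT value, but the documents do not support that. Section 2.1.5 has a specific pre-granule rule for switchers, and the End of Core SAP combined the same rule with the same windows. What remains under that reading is a conflict between a generic row and a specific rule.

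The reply does not remove the defect. The final SAP states one origin, and following it gives the wrong by-visit table. Where the final SAP wants a different origin it says so: Table 5-5 counts growth data from the first intake of deferasirox, and 2.7.7.1 sets a core-phase baseline for both groups. Table 5-7 has no such statement. The programming specifications may settle the matter, but they are a separate document and not available here.

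Three limits on the impact do stand:
- Worst post-baseline analyses ignore windows (5.3.4), and listings keep all data. Lens opacity (LOCSIII) grades are summarised as worst change, so only lens image quality is affected (2.7.6.4).
- The End of Core SAP already planned site-assessed ocular results on Safety Set 4, on a clock that fits. All patients had completed the core phase by 18-Dec-2018 and its cut-off was 18-Jan-2021, so scheduled first-year extension examinations precede that cut-off.
- These are descriptive safety displays. Table 4-1 of the final SAP says that no comparison between the cross-over and granule groups is planned for the entire granule period.

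**Conclusion.** The point holds for the final SAP as written. For every cross-over patient examined on schedule, the first annual extension examination (granule day 365, range 335 to 395) falls in no weekly window, and each later one moves to the preceding label. The result rests on the literal definition of study treatment and on granules starting at Visit 17.

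A reader might infer that the whole cross-over group's first-year eye data are lost. The documents do not support that. The examination still enters EOT_Ext if it is the end-of-treatment examination, or the last available value when none was done, and it still counts in worst-value tables and listings. A reader might also infer that later labels are a year wrong. They are so only against the visit schedule: day 729 under Week 101 (planned day 701) is close to true time on granules. The main defects are the missing first-year window and an unstated day origin. Both are worth correcting, but neither bears on the trial's primary conclusions.

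**What to change.** State the reference date for day 1 under both Table 5-6 and Table 5-7, separately for cross-over and granule patients where they differ. For Table 5-7, choose one of these:

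- **(a) Core clock or scheduled visit.** Count ocular windows from the first core dose, or index them on Visit 33 and each annual visit. Days 701, 1065, 1429 and 1793 then fall in their own windows, and both groups' Visit 33 appears in the same column.
- **(b) Granule clock for cross-over patients.** Add k = 12: (5 + 48 − 1) × 7 + 1 = day 365, window 306 to 423, which covers 335 to 395. Continue every 364 days (planned days 729, 1093 and 1457), and label the columns as time on granules.

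In either case, state that the change-from-baseline reference for cross-over patients stays the pre-granule value of 2.1.5, whatever the generic Baseline row says. The cost is a footnote under each table and, under (b), a revised window row. No new data are needed, and worst-value outputs do not change.
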